## Study Summary

Title	Open-label Phase 1/2 Study with a Single Arm of Interferon Gamma-1b Treatment of Osteopetrosis
Study Sponsor	[name], MS Assistant Professor, Pediatric Endocrinology David Geffen School of Medicine Los Angeles Biomedical Research Institute at Harbor-UCLA Medical Center
Principal Investigator (PI)	[name], MS Assistant Professor, Pediatric Endocrinology David Geffen School of Medicine Los Angeles Biomedical Research Institute at Harbor-UCLA Medical Center
Study Design	multi-center open-label phase 1/2 clinical trial
Study Duration	Subjects will participate in the study for 1 year. It is expected that enrollment will be completed in 18 months and the last subject will complete the protocol 2.5 years after study initiation.
Study Center(s)	
 
1. LABioMed at Harbor-UCLA [name] [name]
 
2. University of Minnesota [name] [name]
 

Study Objectives	
 
1. To determine the feasibility and tolerability of interferon gamma-1b treatment in patients with intermediate osteopetrosis.
 
2. To determine the safety and efficacy of interferon gamma-1b in patients with intermediate osteopetrosis.
 

Study Endpoints	
Primary Endpoint: The primary objective of this pilot study is to determine the feasibility and tolerability of interferon gamma-1b treatment for 1 year in patients with intermediate osteopetrosis. Specifically, i) the ability to enroll patients, and ii) continued treatment throughout the 1-year observational period.
 
Secondary Endpoints: The secondary objectives of this study will focus on change in immunologic and hematologic function, bone mineral density and osteoclast function, physical function and quality of life.

Number of Subjects	10
Main Inclusion Criteria	
 
• Intermediate Osteopetrosis, defined as: 
 
○ Anemia, or
 
○ Neutropenia, or
 
○ <math>\geq 1</math> serious infection over prior year defined as requiring hospitalization and/or IV antibiotics, or
 
○ History of impaired bone healing
 
 
 
• Age <math>> 1</math> year
 

Duration of Observation	1 year

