### 4.2 Secondary Hypotheses

The secondary hypotheses are:

1. Compared to baseline, treatment with IFN- $\gamma$ 1b will result in:
  - a. Decreased tibial volumetric bone mineral density (**vBMD**) and estimated bone strength measured by peripheral quantitative computed tomography (**pQCT**);
  - b. Decreased total body and lumbar spine areal BMD (**aBMD**) by dual-energy x-ray absorptiometry (**DXA**);
  - c. Increased levels of markers of bone remodeling (see Table 1);
  - d. Increased osteoclast activity by *in vitro* testing;
  - e. Increased white blood cell (**WBC**) and platelet counts in patients that have lower than expected blood counts at baseline.
  - f. Increased height standard deviation score (**SDS**) for participants <18 years with open growth plates;
  - g. Decreased inflammation measured by erythrocyte sedimentation rate (**ESR**);

[figure not shown]
- h. Decreased pain score (based on prior 4 weeks);
  - i. Increased physical function score (based on prior 4 weeks); and
2. Compared to the 12 months prior to study entry (based on medical record review or subject recollection), treatment with IFN- $\gamma$ 1b over 12 months will result in:
  - a. Decreased number of hospitalizations for infection;
  - b. Decreased number of days treated with antibiotics;
  - c. Beneficial change in WBC and platelet counts in patients who have lower than expected blood counts at baseline;
  - d. Beneficial change in ESR;
  - e. Increased height SDS for participants  $<18$  years with open growth plates; and
3. Patients will not develop neutralizing antibodies.

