# **7 Data Collection and Analysis**

## **7.1 Subject Population(s) for Analysis**

- Treatment-compliant population: Any subject who received at least 85% of prescribed doses and attended all scheduled study visits.
- Safety population: All subjects who receive any amount of treatment.

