## 7.2 Statistical Methods

### 7.2.1 Sample size Determination

This is a pilot study to obtain data for a larger, definitive clinical trial. The sample size of 10 was determined based on feasibility estimates including potential screening failures

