### 7.2.2 Statistical Analysis

Descriptive analyses of baseline characteristics and outcomes will include means and standard deviations for continuous variables and frequencies for categorical variables. Confidence intervals and P-values will be based on a t-distribution. Statistical significance will be considered as  $p < 0.05$ . The primary endpoint and safety analyses will be primarily descriptive reporting the number and percentage of compliance and AEs. The secondary endpoints for hematologic function, immune function, and bone mineral density will be evaluated by paired t-tests or chi-squared to evaluate change from baseline to 12 months. Secondary endpoints related to in vitro osteoclast assays will be descriptive.

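### The only confidence-interval rule is a t-distribution not limited to means, which would fail for this trial's key proportions at n=10, and chi-squared is named for within-subject change without a paired version

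*Combined protocol and SAP*

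**What the plan says.** Section 7.2.2 contains the whole analysis plan. It calls for means and standard deviations for continuous variables and frequencies for categorical ones, and then states: "Confidence intervals and P-values will be based on a t-distribution". The primary endpoint and safety analyses are "primarily descriptive reporting the number and percentage of compliance and AEs". For the blood, immune and bone-density outcomes among the secondary endpoints, the rule is that they "will be evaluated by paired t-tests or chi-squared to evaluate change from baseline to 12 months". The Study Summary repeats these rules and adds physical function and quality of life to the tested list.

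Several results of interest are proportions:

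- One part of the primary endpoint is "continued treatment throughout the 1-year observational period" (Study Summary, Study Endpoints).
- Section 7.1 defines the treatment-compliant population as "Any subject who received at least 85% of prescribed doses and attended all scheduled study visits", so compliance is a yes/no variable.
- Section 4.2, hypothesis 3, is "Patients will not develop neutralizing antibodies".

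Section 7.2.1 gives the purpose, "This is a pilot study to obtain data for a larger, definitive clinical trial", and the basis for the size: "The sample size of 10 was determined based on feasibility estimates including potential screening failures".

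**The concern.** Two things are left open.

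**Intervals.** The t-distribution sentence directly follows one that covers both continuous and categorical variables, and no other interval rule is given. The results hoped for lie near 10/10 (continuing, compliant) and 0/10 (neutralizing antibodies). A t interval on 0/1 data collapses to zero width at exactly those counts. Someone planning the larger trial could then read 0/10 as excluding neutralizing antibodies, when the data would be compatible with a true rate of about 31%.

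**Test.** The word paired is attached only to the t-tests. Baseline and month 12 come from the same subjects, so a yes/no outcome would need a paired test. Chi-squared could mean Pearson's test on the two margins or McNemar's test, and McNemar's has asymptotic, mid-p and exact versions. At n=10 these can fall on different sides of 0.05, so the version should be chosen before the data are seen.

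**Working it through.** **Inputs.** n=10 (section 7.2.1); significance at p<0.05 (section 7.2.2), taken as two-sided because sidedness is not stated. The sample size rests on feasibility, with no power, effect size or expected rate, so there is no plan figure to reproduce. The true rates and paired tables below are assumptions.

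**Step 1: the t rule applied to x/10.** With p = x/10, the standard error of the mean of 0/1 data is sqrt(p(1−p)/9), and t(0.975, 9 df) = 2.262.
- 9/10: sqrt(0.09/9) = 0.100; 0.9 ± 2.262 × 0.100 = 0.674 to 1.126.
- 8/10: sqrt(0.16/9) = 0.133; 0.8 ± 2.262 × 0.133 = 0.498 to 1.102.
- 10/10 and 0/10: the standard error is 0, so the interval has zero width.

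**Step 2: intervals made for proportions.** Clopper-Pearson limits are beta quantiles. At 10/10 the lower limit is 0.025^(1/10) = 0.6915; at 0/10 the upper limit is 1 − 0.6915 = 0.3085. Wilson uses z = 1.96.

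| Count | t | Clopper-Pearson | Wilson |
|---|---|---|---|
| 0/10 | 0-0% | 0-31% | 0-28% |
| 8/10 | 50-110% | 44-97% | 49-94% |
| 9/10 | 67-113% | 55.5-99.7% | 60-98% |
| 10/10 | 100-100% | 69-100% | 72-100% |

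The t interval has zero width or leaves 0-100% for 8 of the 11 possible counts (0-3 and 7-10). It is usable only for 4, 5 and 6.

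**Step 3: coverage.** Sum the Binomial(10, p) probabilities over the counts whose interval contains p. For example, at p = 0.90 the t interval contains 0.90 only for counts 6 to 9: 0.0112 + 0.0574 + 0.1937 + 0.3874 = 0.650. Most of the shortfall is the 10/10 result, which has probability 0.349.

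| Assumed true rate | t | Clopper-Pearson | Wilson |
|---|---|---|---|
| 80% | 88.6% | 99.4% | 96.7% |
| 90% | 65.0% | 98.7% | 93.0% |
| 95% | 40.1% | 98.8% | 91.4% |

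**Step 4: versions of the test.** Pearson compares the two margins as if they were independent groups of 10. With b and c the numbers changing in each direction, ordinary McNemar is (b−c)²/(b+c) on 1 df, exact McNemar is twice the binomial tail at 0.5 on b+c changes, and mid-p subtracts the point probability from the exact value.

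| Change | Pearson | Ordinary McNemar | Mid-p | Exact |
|---|---|---|---|---|
| 0/10 to 4/10 | 0.025 | 0.0455 | 0.0625 | 0.125 |
| 0/10 to 5/10 | 0.010 | 0.025 | 0.031 | 0.0625 |

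Over all 286 possible paired tables with n=10, Pearson is significant in 72, ordinary McNemar in 68, mid-p in 54 and exact in 36. Pearson and ordinary McNemar disagree in both directions: Pearson alone in 14, McNemar alone in 10. These are counts of tables, not probabilities.

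**Step 5: false positives.** With no true change and non-negative correlation between baseline and month 12, Pearson's type I error peaks at about 4%, against 5.3% for ordinary McNemar. Pearson exceeds 5% (up to 13%) only if negative correlation is allowed.

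**The case against.** The t-distribution sentence cannot be meant for everything, because the same paragraph prescribes chi-squared, whose p-value is not t-based. The natural reading is that it concerns means. For the primary endpoint and safety the plan offers numbers and percentages, and it promises no interval for continuation, compliance, neutralizing antibodies or adverse events. This stands: the zero-width intervals and the 40% coverage describe what would happen if the rule were used for proportions, not an analysis the plan commits to. What remains is that no other rule exists if an interval is wanted, and a pilot meant to inform a larger trial has good reason to want one.

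On the test, chi-squared may well mean McNemar, and no yes/no outcome is assigned to it; most secondary endpoints are continuous or counts. This also stands.

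A reader might infer that an unpaired test would inflate false positives, or that ignoring the pairing by itself changes the conclusion. Neither is supported. Pearson is conservative under the usual non-negative correlation, and ordinary McNemar is also below 0.05 in both examples. The changes of conclusion come from choosing a mid-p or exact version. The argument for naming a paired test is that it matches the design and settles the version in advance.

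**Conclusion.** The concern holds as a minor point. The plan's only interval rule is unsuitable for proportions near 0 or 1 at n=10, where its key proportions are hoped to fall, and the categorical test is not fully specified. If t intervals were reported, 10/10 would read 100-100% instead of 69-100%, and 0/10 would read 0-0% instead of 0-31%. Coverage would be about 89%, 65% and 40% at true rates of 80%, 90% and 95%; these rates are assumed, as the documents give none.

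The consequence is conditional on intervals being reported for proportions and on a paired yes/no outcome being tested. No decision or stopping rule depends on either. A reader might conclude that the primary analysis is invalid; it is not, because counts and percentages are sound as description.

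**What to change.** In section 7.2.2 and in the Statistical Methods entry of the Study Summary:

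1. Limit the t-distribution sentence to mean changes in continuous measures.
2. Keep the counts and percentages, and add 95% Clopper-Pearson intervals (Wilson is acceptable) for continued treatment to month 12, compliance as defined in section 7.1, and neutralizing antibodies, and for any adverse-event percentage given with an interval.
3. Replace chi-squared with McNemar's test in one version fixed in advance (exact or mid-p), naming the paired yes/no outcomes it covers. Delete it if there are none.

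The cost is two or three sentences in two places, with no new data or subjects. The exact intervals will look wide: 0/10 reaches 31%, and with 8 evaluable subjects 0/8 reaches 1 − 0.025^(1/8) = 37%. Exact McNemar needs at least 6 changes, all in one direction, for p<0.05 (5 changes give 0.0625, 6 give 0.031); mid-p needs 5 (0.031). Power will therefore be lower than with Pearson, and the plan should say so.

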## 8 Safety and Adverse Events

### 8.1 Definitions

#### *Adverse Event*

An adverse event (AE) is any symptom, sign, illness or experience that develops or worsens in severity during the course of the study. Intercurrent illnesses or injuries will be regarded as AEs. Abnormal results of laboratory or diagnostic procedures are considered to be AEs if the abnormality:

- Results in study withdrawal
- Is associated with a serious adverse event (SAE)
- Is associated with clinical signs or symptoms
- Leads to additional treatment or to further diagnostic tests
- Is considered by the Investigator to be of clinical significance.

#### *Serious Adverse Event (SAE)*

An SAE is any AE that is:

- Fatal

- Life-threatening
- Requires or prolongs a hospital stay
- Results in persistent or significant disability or incapacity
- A congenital anomaly or birth defect

Important medical events are events that may not be immediately life-threatening, but are clearly of major clinical significance and may be SAEs. They may jeopardize the subject, and may require intervention to prevent one or the other serious outcomes noted above.

#### *Hospitalization*

Hospitalization shall include any initial admission (even if less than 24 hours) to a healthcare facility as a result of a precipitating clinical adverse effect; to include transfer within the hospital to an intensive care unit. Hospitalization or prolongation of hospitalization in the absence of a precipitating, clinical adverse effect (e.g., for a preexisting condition not associated with a new adverse effect or with a worsening of the preexisting condition; admission for a protocol-specified procedure) is not, in itself, a serious adverse effect.

#### *Expected Adverse Event*

Expected AEs are those that are known to be associated with or have the potential to arise as a consequence of participation in the study. This will include any AE or SAE that are expected consequences of having osteopetrosis or receiving treatment with IFN- $\gamma$ 1b described in Section 8.4.4.

#### *Unexpected Adverse Event*

An AE or suspected adverse reaction is considered unexpected if it is not listed in the drug package insert or Protocol at the specificity or severity that has been observed.

#### *Unanticipated Problems Involving Risk To Subjects or Others (UPIRTSO)*

An AE that in the opinion of the PI is unexpected, related to the study procedures, and serious.

## **8.2 Recording of Adverse Events**

At each contact with the subject, the Investigator/study coordinator must seek information on AEs by specific questioning and, as appropriate, by examination. Information on all AEs should be recorded immediately in the source document, and also in the appropriate AE module of the case report form (**CRF**). All clearly related signs, symptoms, and abnormal diagnostic procedures resulting from a single clinical condition should be recorded individually in the source document and listed under the

single unifying diagnosis. (For example, fever, rigors, sore throat, and high neutrophil count might all be listed under a diagnosis of pharyngitis.)

All AEs occurring during the study period must be recorded. The clinical course of each event should be followed until resolution, stabilization, or until it has been determined that the study treatment or participation is not the cause. Serious adverse events that are still ongoing at the end of the study period must be followed up to determine the final outcome. Any SAE that occurs after the study period and is considered to be possibly related to study participation should be recorded and reported immediately.

AEs will be classified according to the National Cancer Institute (NCI) Common Toxicity Criteria (CTC) V 4.1 and causality will be classified as:

Unrelated - The AE is clearly NOT related to study procedures

Unlikely - The AE is doubtfully related to study procedures

Possible - The AE may be related to study procedures

Probable - The AE is likely related to study procedures

Definite - The AE is clearly related to study procedures

### **8.3 Reporting of Serious Adverse Events**

#### **8.3.1 Study Sponsor Notification by Investigators**

An SAE must be reported to the study PI by telephone, fax, or email (preferred) within 24 hours of the event. An SAE Form must be completed by the Investigator and faxed or emailed to the study Sponsor within 24 hours. The Investigator will keep a copy of this SAE form on file at the study site. Report SAEs by phone, fax or email to:

[name], MS    [contact] (telephone)  
                                  [contact] (facsimile)  
                                  [contact]

At the time of the initial report the following information should be provided:

- Study Identifier
- Study Center

- Subject Number
- A description of the event
- Date of onset
- Current Status
- The reason why the event is classified as serious
- Investigator assessment of the association between the event and study procedures

Within the following 48 hours, the Investigator must provide further information on the SAE in the form of a written narrative. This should include a copy of the completed SAE Form, and any other diagnostic information that will assist the understanding of the event. Significant new information on ongoing SAEs should be provided promptly to the study PI.

### **8.3.2 IRB Notification by Investigators**

Reports of all SAEs (including follow-up information) must be submitted to the IRB within 10 working days if it falls under the UPIRTSO guidelines (unexpected and related to study drug). All deaths, regardless of expectedness or causality, must be reported to the IRB within 10 working days. Copies of each report and documentation of IRB notification and receipt will be kept in the Clinical Investigator's binder.

### **8.3.3 UPIRTSO Events**

Investigators are required to submit a report of UPIRTSO events to the IRB within 10 working days of first learning of the event.

### **8.3.4 Pregnancy**

If a female subject becomes pregnant during the study, she will be withdrawn from the study immediately. Though pregnancy is not by definition an SAE, it will be subject to SAE reporting requirements.

Though the subject will be withdrawn from the study, permission to record survival and adverse event (malignancy, hospitalization for infection) data for the mother to the end of the pregnancy and of survival data for the baby at birth will be requested.

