#### **5.4.7 Participation of Females**

The fetal risks associated with IFN- $\gamma$ 1b are not known, but pre-clinical animal data demonstrate some risk (Pregnancy category C). Females of childbearing potential must agree not to become pregnant during the study and must have a pregnancy test at each study visit (baseline, month 3, month 6, and month 12). Because of the risk involved, sexually active subjects and their partners must use two methods of birth control. They must continue to use both methods until 1 month after stopping study drug. Two of the birth control methods listed below may be chosen:

- Hormonal contraception

- Male or female condoms with or without a spermicidal
- Diaphragm or cervical cap with a spermicidal
- Intrauterine device (IUD)

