**Severe Vitamin D deficiency: total 25-OH vitamin D <10 ng/ml: obtain PTH and serum calcium levels.**

Age	Vitamin D	For all patients with severe vitamin D deficiency: Calcium (elemental) max dose 2000 mg/day Start at higher dose and taper over 4 weeks to AI.
0-1 years	2,000 IU/d x 8 weeks	30-75 mg/kg/day divided 2-4 times daily
1-3 years	2,000 IU/d x 8 weeks	30-75 mg/kg/day divided 2-4 times daily
4-8 years	4,000 IU/d x 8 weeks	30-75 mg/kg/day divided 2-4 times daily
>8 years	50,000 IU/wk x 8 weeks (Rx)	30-75 mg/kg/day divided 2-4 times daily

For post-menarchal female patients, a urine pregnancy test will be performed at Screening and before the Baseline, Month 3, and Month 6 visits. Plasma and serum will be collected as described in Table 1. Immunologic phenotyping will be performed by University of Minnesota. BAP, P1NP, OPG, CTX, TRAP5b, RANKL, and CK-BB will be performed by the Fairview Cytokine Reference Laboratory at the University of Minnesota. Expression, methylation, and genotype data will be generated at LABioMed in the laboratories of Drs. [name] and [name].

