**APPENDIX B**

Schedule of Events (next page)

Schedule of Events										If ADA Positive	
	Screening a	Baseline	time from 1 st IFN- $\gamma$ 1b dose							time from last IFN- $\gamma$ 1b dose	
			3 weeks ( $\pm$ 2 days)	4 weeks ( $\pm$ 2 days)	6 weeks ( $\pm$ 2 days)	3 months ( $\pm$ 1 week)	6 months ( $\pm$ 1 week)	9 months ( $\pm$ 1 week)	12 months ( $\pm$ 1 week)	2-3 weeks	every 4-6 weeks
General											
Medical history	X	X				X	X		X		
Physical exam		X				X	X		X		
Genotype b		X									
RNA and DNA samples		X f				X	X		X		
Anthropometric measurements	X	X f				X	X		X		
Safety Measuresc											
Basic metabolic panel (BMP)	X	X		X	X	X	X	X	X		
Liver function tests (LFT)	X	X		X	X	X	X	X	X		
Urine pregnancy test (UPT) e	X	X				X	X	X	X		
Urinalysis (UA)	X	X		X	X	X	X	X	X		
ECHO with interpretation	X										
EKG with interpretation	X										
Anti-drug antibodies (ADA)			X	X	X	X	X		X	X	X
Bone Biomarker Testingd,g											
Formation Testing (bone specific alkaline phosphatase [BAP], type 1 procollagen [P1NP])	-	X				X	X		X		
Resorption testing (C-telopeptide [CTX], Tartrate resistant acid phosphatase type5b [TRAP5b])	-	X				X	X		X		
RANKL, OPG, CK-BB	-	X				X	X		X		
Endocrine Assessment											
Total 25-OH Vitamin D (25OHD)	-	X			X	X	X		X		
Serum ionized calcium	-	X				X	X		X		
Urine calcium: creatinine	-	X				X	X		X		
Intact parathyroid hormone (iPTH)	-	X				X	X		X		
Inflammatory/Immunology											
CBC with differential and platelets	-	X f				X	X		X		
Erythrocyte sedimentation rate (ESR)	-	X f				X	X		X		
Immunologic phenotyping (CD3, 4, 8, 14, 15, 16, 19, 34, 56) g	-	X				X	X		X		
Neuropsychological testing											
Pain assessment	-	X				X	X		X		
Quality of life survey	-	X				X	X		X		
Orthopedic assessment											
Dual energy X-ray absorptiometry (DXA) lumbar spine, total body, total hip and femoral neck (adults $\geq$ 18yrs only)	-	X				-	-		X		
Peripheral Quantitative CT (pQCT) left tibia	-	X				-	X		X		
In vitro osteoclast function assays – [name] Labh											
Gene expression – osteoclast marker genes	-	X				X	X		X		
Osteoclast activity – ability to release calcium phos from coated plate	-	X				X	X		X		
Infectious outcomes											
Number of hospitalizations in prior 3 months	-	X f				X	X		X		

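### Pregnancy follow-up in Section 8.3.4 does not ask about birth defects or cover the month after the last dose, and four places disagree on the pregnancy-test visits

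*Combined protocol and SAP*

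**What the plan says.** Section 5.4.7 states that the human fetal risk is unknown, that animal data show some risk, and that the drug is in Pregnancy category C. On contraception it adds: "They must continue to use both methods until 1 month after stopping study drug". The SAE list in Section 8.1 includes "A congenital anomaly or birth defect".

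Section 6.4 sends pregnancy follow-up to Section 8.3.4. There, a female subject who becomes pregnant while in the study is withdrawn at once and the pregnancy is handled under the SAE reporting requirements. The plan then says that, with permission, survival and two types of adverse event (malignancy and admission for infection) "data for the mother to the end of the pregnancy and of survival data for the baby at birth will be requested".

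The test visits appear in four places:
- Section 5.4.7: subjects "must have a pregnancy test at each study visit (baseline, month 3, month 6, and month 12").
- Section 6.3.2, below the vitamin D tables: "a urine pregnancy test will be performed at Screening and before the Baseline, Month 3, and Month 6 visits".
- Table 1 marks screening, baseline and months 3, 6 and 12. The test sits in the safety block, whose footnote c adds safety labs at weeks 4 and 6 and month 9.
- Appendix B marks screening, baseline and months 3, 6, 9 and 12. Its two columns after the last dose are empty for this test.

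**The concern.** The harm named in Section 5.4.7 is harm to the fetus, but the items requested in Section 8.3.4 do not measure it. The two maternal event types are the same two that Section 6.8 uses for subjects who withdraw consent, and neither describes how a pregnancy ended. Survival at birth does not separate a healthy infant from one with an anomaly. If an exposed pregnancy occurs, the most relevant information may not be recoverable later, because the mother has left the study and the permission sought from her does not name it.

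Two related gaps affect detection. The contraception rule implies that exposure still matters for a month after dosing, yet the reporting trigger stops with the study. In addition, sites reading different sections would test at different visits.

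**Working it through.** The plan gives no figure to reproduce. The check sets the sections side by side and adds one timeline calculation.

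**1. Infant and pregnancy data.**

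| Item | Requested in 8.3.4? |
|---|---|
| Maternal survival, malignancy, admission for infection | Yes, to the end of the pregnancy, with permission |
| Infant survival at birth | Yes, with permission |
| Type of outcome (live birth, loss, termination) | No explicit item |
| Gestational age | No |
| Congenital anomaly or birth defect | No |

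The items that Section 8.3.1 requires in an initial SAE report do not include pregnancy outcome either. The remaining route is Section 8.2. It requires SAEs still ongoing at the end of the study to be followed to their outcome, and SAEs after the study that are possibly related to be recorded and reported. For a birth defect found after the study, that route works only if the investigator learns of the defect and judges it possibly related.

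**2. Month after the last dose.** Inputs: participation of 12 months (Section 5.2), dosing for the remainder of the study if tolerated (Section 6.3.6), contraception for 1 month after stopping (Section 5.4.7), and a month 12 visit window of ±1 week (Table 1). Assumptions: 1 month = 30 days, and the last dose is at month 12.

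- End of contraception period = 12 + 1 = month 13.
- Gap after a month 12 test = 13 − 12 = 1 month, or about 30 days.
- With the visit window: 30 − 7 = 23 days to 30 + 7 = 37 days.
- A subject who stops drug by about month 11 and stays on the visit schedule, as Section 6.8 asks, has no gap: 11 + 1 = 12.

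One contact may fall inside the gap. Table 1 footnote g asks for an antibody sample 2-3 weeks (14 to 21 days) after the last dose. That is 30 − 21 = 9 to 30 − 14 = 16 days before the contraception period ends. No pregnancy test or question is attached to it, and Appendix B heads the column as applying only to antibody-positive subjects.

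**3. Test visits.**

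| Source | Screening | Baseline | Month 3 | Month 6 | Month 9 | Month 12 |
|---|---|---|---|---|---|---|
| 5.4.7 | not listed | yes | yes | yes | no | yes |
| 6.3.2 | yes | yes | yes | yes | no | no |
| Table 1 | yes | yes | yes | yes | unclear (footnote c) | yes |
| Appendix B | yes | yes | yes | yes | yes | yes |

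Footnote c does not settle the matter. Applied to the pregnancy test, it would add weeks 4 and 6 as well as month 9, and Appendix B has no pregnancy test at those weeks. Section 6.3.2 names only the metabolic panel, liver tests and urinalysis at those three visits.

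**The case against.** The strongest reply is that the general safety rules already cover the ground. Pregnancy falls under SAE reporting, a birth defect is an SAE, Section 8.3.1 asks for a narrative and for significant new information on ongoing SAEs, and the post-study rule in Section 8.2 has no end date. This stands to a point. A reader might infer that birth defects would go uncaptured or that reporting stops at month 12, and the documents do not support either. What remains is that capture is passive: nobody is told to ask.

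Four other tempting readings also go too far.
- A reader might infer that pregnancy loss is invisible. The mother is followed to the end of the pregnancy, and a stillbirth would show as non-survival. What is missing is an explicit outcome category.
- A reader might infer that subjects have no contact at all after the last dose. Table 1 footnote g places an antibody sample there, and Section 8.2 requires adverse-event questioning at every contact. What is missing is anything specific to pregnancy.
- A reader might infer from Section 6.3.2 that the second half of the year passes without testing. That rests on one sentence. The same section opens by referring to the Table 1 time points, and Section 5.4.7, Table 1 and Appendix B all include month 12. It may be a drafting omission.
- A reader might infer a 6-month testing gap from Table 1. Footnote c makes that disputable.

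It is also fair to say that few pregnancies are likely among 10 subjects, enrolled from above 1 year of age, with two-method contraception for those who are sexually active. That limits the expected yield. It does not change what would be lost if one occurred.

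**Conclusion.** The point holds in a limited form. Section 8.3.4 does not request information on birth defects, so the outcome closest to the stated fetal risk is not actively sought and could be missed. For subjects dosed to month 12, no pregnancy-specific test or enquiry is scheduled for about 30 days (23 to 37) of the contraception period, and the trigger in Section 8.3.4 does not extend to it. The test visits conflict at months 9 and 12.

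The timeline rests on a 30-day month and a last dose at month 12. Treating the extra month as a period of possible exposure is an inference, since Section 5.4.7 states only a contraception period. The consent pages are not available, so their wording on pregnancy follow-up cannot be judged. This should be corrected because the safety data would be better at little cost. It does not threaten the trial's primary feasibility and tolerability objective.

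**What to change.** 1. In Section 8.3.4, add to the data requested: pregnancy outcome (live birth, loss, termination), gestational age, and any congenital anomaly or birth defect.
2. State that reporting covers pregnancies conceived up to the end of the contraception period in Section 5.4.7. Add one brief pregnancy and adverse-event enquiry by telephone or email at the end of that period. Keep it separate from the post-dose antibody sample, which Appendix B makes conditional on antibody positivity.
3. Reconcile Sections 5.4.7 and 6.3.2, Table 1 with footnote c, and Appendix B on the pregnancy-test visits. Which schedule is right is for the investigators to decide.

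The cost is protocol wording, a few form fields, and one short contact for each post-menarchal subject (at most 10). The downside is that the consent text for pregnancy follow-up must name the added items.
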